# 7.1.3. Analyses for Change from Baseline and Repeated Measured Endpoints

Continuous variables representing neurologic disease progression, such as NIS-CS, NIS-LL, PND, MRC, CMTNS2 and mBMI may be collected at multiple time points. Measures may be reported in the pre-treatment baseline period (at least 6 months (and up to 12 months) before treatment initiation), tafamidis initiation (within 3 months before or after treatment initiation), and post-treatment (at least 6 months after treatment initiation with a ±3-month window) as population mean, SD, median, first and third quartiles, and range in a table or chart format. If a participant had multiple values in one or more of the pre-defined periods, the mean value will be used in calculating the population-level summary statistics. More details of the number of assessments and assessment schedule will be finalized once the data structure is known.

PND and CMTNS2 scores will be summarized using a frequency table for both the pre-treatment and tafamidis treatment periods. Additionally, a shift table will be used to capture the change in PND and CMTNS2 scores between the two periods. The shift table will capture the changes at each visit relative to start of the period, ie, baseline for the pre-treatment period and tafamidis initiation visit for the tafamidis treatment period (within 3 months before or after treatment initiation).

#### 7.2. Statistical Analyses

For the primary and secondary objectives, neurologic function, ie, NIS-CS, NIS-LL, MRC, CMTNS2, and mBMI will be examined in the full analysis set. If there is a sufficient number of patients with at least three neurologic assessments a linear mixed-effect model will be conducted to compare the rate of disease progression (within patient) between pre-treatment and tafamidis treatment periods. Patients must have at least three assessments to be included in the linear mixed-effect model (one in the pre-treatment period, one in the tafamidis treatment period, and one additional that can be in either pre-treatment or in the tafamidis treatment period). The linear mixed-effect model includes pre-treatment baseline score, treatment period, and their interactions with time as fixed effects, and the time-slope and intercept for each patient are included as random effects. Time is defined as number of months from pre-treatment baseline. The estimates of the monthly rate of change, along with the 95% confidence interval and the p value associated with the within group comparison comparing the pre-treatment and tafamidis treatment periods will be summarized.

However, if there is not a sufficient number of patients with at least three neurologic assessments, and many patients only have two assessments, then an approach is to take the first measurement and the measurement that fell within the window of the measurement in which majority of the patients had for the post-treatment assessment (whether they only have two or three or more) and test for significant statistical differences between the two assessments using an unpaired, or independent samples, t-test.

Alternatively, in the event there is an insufficient number of patients with three or more neurologic assessments, separate subgroup statistical analyses may be performed. This approach may use a between-subjects analysis of variance (ANOVA) for patients with at least three neurologic assessments and conduct unpaired, or independent samples, t-test for

patients with only two neurologic assessments. Descriptive summaries will be provided by treatment (pre-treatment or post-treatment), or by subgroups (if data permits) for each neurologic function endpoint.

It is anticipated that there will be patients who do not satisfy inclusion criteria for pre and post treatment comparisons for various reasons such as not being on treatment for at least 6 months (with ±3-month window) because they passed away, not having a pre-treatment or post-treatment neurologic assessment, not having a NIS score or other missing data points and/or reasons. While pre and post treatment comparisons cannot be conducted for these patients, descriptive statistics on the composite score and/or its sub-scale will be reported to characterize patient and treatment characteristics.

Additional post-hoc analyses of final data from this study may be performed against final data from comparable tafamidis-treated and untreated ATTRv mixed phenotype patients from the Transthyretin Amyloidosis Outcomes Survey (THAOS; Pfizer Study B3461001). If performed, analysis methods will be provided as part of an amendment to this SAP.

All data analysis will be executed using statistical software SAS version 9.4.

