## 5. AMENDMENTS AND UPDATES

Amendment number	Date	Protocol section(s) changed	Summary of amendment(s)	Reason
Amendment 1	01/09/23	1-6, 9, 11	Administrative amendment:  Number and timing of measurements changed to address data availability.  Addition of CMTNS2 instrument.  Updated template language for data analysis  Updated AE reporting language per SOP	Change in PIs and available data. Not expecting most patients to have multiple measures before or after treatment.
Amendment 2	31 May 2023	Inclusion Criteria, Section 9.21	Changed criteria number 4 from "≥2: to "≥1"	Administrative, typographical error
Amendment 2	31 May 2023	Table 9-2, Clinical Outcomes	Deleted footnote to align with SAP	Administrative

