#### 9.2.1. Inclusion Criteria

Patients must meet all the following inclusion criteria to be eligible for inclusion in the study:

- 1. Age ≥18 years at diagnosis.
- 2. Diagnosed with ATTRv-CM, mixed phenotype.
- 3. Treated with tafamidis (VYNDAQEL 80 mg [four 20-mg tafamidis meglumine capsules] orally once daily or VYNDAMAX 61 mg [one 61-mg tafamidis capsule] orally once daily) for ≥6 months.
- 4. Have had ≥1 pre- and ≥1 post-treatment neurologic assessments.\*

\*The pre-treatment neurological assessment will be at least 6 and up to 12 months prior to treatment initiation. The baseline assessment will be within 3 months before or 3 months after the start of tafamidis treatment. In the absence of baseline data within a+/-3 month window, structured data from exam notes may also be retrieved if available to align with real world practice. The post-treatment period will be at least 6months after treatment initiation.

Note: As this study involves anonymized structured data, which according to applicable legal requirements do not contain data subject to privacy laws, obtaining informed consent from patients is not required.

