# Inclusion criteria

- Age ≥18 years at diagnosis
- Diagnosed with hereditary ATTR-CM, mixed phenotype
- Treated with tafamidis (VYNDAQEL 80 mg [four 20-mg tafamidis meglumine capsules] orally once daily or VYNDAMAX 61 mg [one 61-mg tafamidis capsule] orally once daily) for ≥6 months (with a ± 3-month window)
- Have had ≥1 pre- and ≥2 post-treatment neurologic assessments\*+

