#### 4. ANALYSIS SETS/POPULATIONS

#### 4.1. Full Analysis Set

The study will include all patients with mixed-phenotype ATTRv-CM who meet the study protocol I/E criteria and are treated with tafamidis, as either VYNDAQEL 80 mg (four 20-mg tafamidis meglumine capsules) orally once daily or VYNDAMAX 61 mg (one 61-mg tafamidis capsule) orally once daily for at least 6 months (with a ±3-month window). All patients meeting the below study enrollment criteria will be included in the full analysis dataset. It is estimated that at least 30 patients will be included in the analysis.

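### The mixed model excludes eligible two-assessment patients, and an undefined trigger replaces it with unpaired tests on paired data

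*SAP*

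**What the plan says.** - **Analysis set.** SAP 7.2 says the neurologic endpoints and mBMI "will be examined in the full analysis set". SAP 4.1 defines that set as patients "who meet the study protocol I/E criteria".
- **Eligibility.** Criterion 4 in Protocol 9.2.1 reads "Have had ≥1 pre- and ≥1 post-treatment neurologic assessments". The SAP's inclusion list reads "Have had ≥1 pre- and ≥2 post-treatment neurologic assessments". These conflict.
- **Entry to the model.** SAP 7.2: "Patients must have at least three assessments to be included in the linear mixed-effect model". One value must be pre-treatment, one on treatment, and the third may fall in either period.
- **Trigger.** SAP 7.2: "If there is a sufficient number of patients with at least three neurologic assessments a linear mixed-effect model will be conducted". No threshold is stated.
- **If the trigger is not met.** SAP 7.2 offers an unpaired t-test between two assessments. Alternatively, it offers a between-subjects ANOVA for patients with three or more values plus unpaired t-tests for those with two.
- **Possible third value.** Protocol 9.2.1 describes a visit near initiation: "The baseline assessment will be within 3 months before or 3 months after the start of tafamidis treatment". Criterion 4 does not require it.

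**The concern.** A likelihood-based mixed model does not need the same number of values from every patient. Two-visit patients still inform the fixed effects and variances. The three-value rule therefore makes the modelled set smaller than the set the SAP says it will analyse, and selects it by how often patients were examined in routine practice.

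The open trigger is the larger problem. Three analyses are available, and the choice among them is made once the visit counts are known. P-values are reported at 0.05 without multiplicity adjustment (SAP 3.1 and 3.2).

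The alternatives also treat repeated values from one patient as if they came from different patients. Such a test is too conservative. In a study of progression that matters in a particular way: a real worsening may come out non-significant and be read as stability.

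**Working it through.** The documents give no power calculation, SD, within-patient correlation or share of patients with three values, so there is no planned figure to reproduce. The only stated number is an estimate of at least 30 patients (Protocol 9.5, SAP 4.1). Everything else below is an assumption.

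**1. Who enters the model.** Under the Protocol criterion, 1 + 1 = 2 assessments are enough, so the rule can exclude eligible patients. Under the SAP list, 1 + 2 = 3, so it excludes nobody. SAP 4.1 points to the Protocol criteria, and SAP 7.2 itself plans for many patients having only two values, which could not occur under the SAP list. If 20%, 30%, 50% or 70% of 30 have three values, 6, 9, 15 or 21 enter the model and 24, 21, 15 or 9 are left out.

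**2. Unpaired test on paired data.** With equal SD σ at both times and n pairs:

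- correct SE of the mean change: σ√(2(1−ρ)/n)
- SE used by the unpaired test: σ√(2/n)
- ratio: 1/√(1−ρ)

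Paired power uses the noncentral t with n−1 = 29 degrees of freedom and noncentrality d/√(2(1−ρ)/n), where d is the difference in SD units:

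- ρ 0.5, d 0.5: 0.5/√(1.0/30) = 2.74
- ρ 0.7, d 0.3: 0.3/√(0.6/30) = 2.12
- ρ 0.8, d 0.3: 0.3/√(0.4/30) = 2.60

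Power of the unpaired test on the same data was simulated (two-sided 0.05):

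| ρ | d | SE ratio | Paired power | Unpaired power |
|---|---|---|---|---|
| 0.5 | 0.5 | 1.41 | 75% | 47% |
| 0.7 | 0.3 | 1.83 | 54% | 8% |
| 0.8 | 0.3 | 2.24 | 71% | 5% |

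The real type I error of the unpaired test is below 1% at ρ 0.5 and below 0.1% from ρ 0.7, against a nominal 5%.

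**3. What the two-visit patients add.** I used generalised-least-squares information for a two-slope model with random intercept and slope, a simplification of the SAP model with no baseline covariate. Visits were at 6–12 months before, within 3 months of, and 6–15 months after initiation. Assumed (intercept SD, slope SD per month, residual SD): (15, 0.5, 5), (15, 1, 3) and (15, 0.3, 8). The table gives the SE with three-visit patients only, divided by the SE with all 30:

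| Three visits, of 30 | Difference in rates | On-treatment rate |
|---|---|---|
| 6 | 1.00–1.17 | 1.28–1.78 |
| 9 | 1.01–1.10 | 1.19–1.58 |
| 15 | 1.01–1.05 | 1.11–1.32 |
| 21 | 1.02–1.03 | 1.06–1.16 |

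Over a wider range (intercept SD 20, slope SD 0.2–1.0, residual SD 3–10, post visits from 3–9 up to 3–24 months), the SE of the difference falls by about 2 to 16% with 10 of 30 having three visits. It dips to about 1% where slopes vary most and residual noise is least. With 20 of 30 it falls by 0 to 5%.

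**4. Baseline as covariate.** The SAP model has the pre-treatment score as a fixed effect. If that score is only a covariate, a two-visit patient contributes one outcome value and no slope, so opening the model would achieve little.

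**The case against.** **Three visits have a rationale.** The SAP's comparison is of rates within a patient, and one value on each side of initiation cannot separate two slopes. This stands. If all 30 patients had only two visits, the SE of the difference in rates would be 1.47 against 0.27 with three visits each (assumed SDs 15, 0.5, 5). It limits the gain from opening the model. It does not justify removing patients who are in the stated analysis set, nor the unpaired tests.

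**Most of the cohort is lost.** A reader might infer this from the amendment table in Protocol 5: "Not expecting most patients to have multiple measures before or after treatment". The documents do not support it. One visit in each of the three windows gives three values with no repeat before or after treatment, and that text is a reason for a change, not a forecast of visit counts. The share is unknown.

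**The subset is biased by severity.** This too goes beyond the documents. Selection by visit frequency is possible, but nothing links frequency to severity, and the wider cohort is already selected on having both assessments and about six months of treatment.

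**The study is exploratory.** SAP 3.1 says so and plans no formal hypothesis testing, and two-visit patients stay in the descriptive summaries. That lowers the stakes. The reported p-values and intervals should still be valid for the data they describe.

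**Conclusion.** The point holds in limited form. Two things are documented: under the Protocol criterion, eligible two-assessment patients are barred from the main model, and an unquantified trigger leads to tests that are wrong for repeated values from the same patients. The second carries most of the harm. The size of its power loss depends on the assumed correlation and difference, but any positive correlation makes the unpaired SE too large.

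The number of patients lost cannot be derived, and if the SAP's inclusion list were the intended one the three-value rule would exclude nobody. Precision is a weak argument for the main contrast and a better one for the separate monthly rates. The case for change rests on covering the stated set, fixing the analysis in advance and respecting the pairing.

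**What to change.** 1. Reconcile criterion 4 between Protocol 9.2.1 and the SAP inclusion list, and state which list defines the full analysis set.
2. Fit the mixed model to every full-analysis-set patient with at least one pre-treatment and one treatment-period value. Keep the pre-treatment score as an outcome in the repeated-measures vector, not only as a covariate. Report the three-or-more subset as a sensitivity analysis.
3. Delete the trigger. Replace the unpaired t-test with a paired test of pre-to-post change, stating that it tests change and not a difference in rates. Replace the between-subjects ANOVA with a repeated-measures model for patients with three or more values.
4. If the random slope does not converge, use a random intercept with robust, small-sample-corrected standard errors, because ignoring varying slopes can understate the SE of the rates.
5. Report how many patients have two, and three or more, values for each endpoint.

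The cost is SAP wording and one extra model run, plus an edit to whichever eligibility list is changed. The downside is that two-visit patients cannot separate the two slopes within a patient and add little to the random-slope variance. If few patients have three values, the rate comparison will stay imprecise and should be reported as such.

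### The first fallback test in SAP 7.2 adds untreated and on-treatment change together, so it does not estimate the change in progression rate that the main model targets

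*SAP*

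**What the plan says.** **Main model.** SAP 7.2 plans a linear mixed model to "compare the rate of disease progression (within patient) between pre-treatment and tafamidis treatment periods". It reports monthly rates of change with a 95% confidence interval and a p-value, and each patient needs at least three assessments.

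**First fallback.** If too few patients have three (no number is given) and many have only two, the SAP suggests that analysts "take the first measurement and the measurement that fell within the window of the measurement in which majority of the patients had" after treatment. The two values are compared with an unpaired t-test. The SAP applies this to patients with two assessments and to those with three or more.

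**Second fallback.** Patients are split by number of assessments: "This approach may use a between-subjects analysis of variance (ANOVA) for patients with at least three neurologic assessments". Those with only two get the same unpaired t-test.

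**Timing.** Protocol 9.2.1 states: "The pre-treatment neurological assessment will be at least 6 and up to 12 months prior to treatment initiation". It adds: "The baseline assessment will be within 3 months before or 3 months after the start of tafamidis treatment". SAP 2.1 and 7.1.3 use the same two windows. They call the earlier one the pre-treatment baseline and the later one the tafamidis initiation assessment. Post-treatment means at least 6 months after initiation. The SAP adds a 3-month allowance either way, the protocol section does not, and neither gives a clear upper limit.

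**Eligibility.** The protocol asks for "Have had ≥1 pre- and ≥1 post-treatment neurologic assessments" and the SAP for "Have had ≥1 pre- and ≥2 post-treatment neurologic assessments". SAP 4.1 defines the full analysis set as patients "who meet the study protocol I/E criteria and are treated with tafamidis", which points to the protocol version.

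**Related text.** The objective (SAP 2.2) concerns neurologic function before and after initiation, while SAP 5.1 names the primary endpoint as neurologic disease progression. SAP 3.1 calls all analyses exploratory but still reports p-values at the 0.05 level. SAP 7.1.3 commits to a shift table for PND and CMTNS2 that takes on-treatment change from the initiation visit.

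**The concern.** The main model asks whether progression slows once tafamidis starts. The fallback asks whether scores differ between a visit well before treatment and a visit some time after it. The SAP moves from one question to the other without saying so. It also leaves out the initiation assessment, which is the visit that separates the two periods, even for patients who have one.

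If the fallback is used, a p-value will be reported for a difference that contains many months of untreated disease. In a progressive disease that can mislead both ways. A drug that stopped progression could appear alongside a significant worsening, and a small difference could reflect slow disease and no drug effect. The two-assessment t-test in the second fallback has the same mix.

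**Working it through.** The documents give no effect size, SD or power calculation, so there is no planned figure to reproduce. The check is what the tested difference can identify.

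**Inputs.** a = months from first visit to initiation, 6 to 12 (Protocol 9.2.1; SAP 2.1, 7.1.3). b = months from initiation to the post-treatment visit: from 6 (protocol), or from 3 with the SAP allowance. Values of b above 6 are illustrative. u and v are the monthly slopes before and after initiation, assumed constant.

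**Step 1: what is tested.** The expected first-to-post difference is D = u·a + v·b. The main model targets v − u. One does not determine the other.

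**Step 2: untreated share of the interval, a/(a + b).**

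| b (months) | a = 6 | a = 12 |
|---|---|---|
| 3 (SAP lower limit) | 6/9 = 67% | 12/15 = 80% |
| 6 | 6/12 = 50% | 12/18 = 67% |
| 9 (if the allowance is read as 6 + 3) | 6/15 = 40% | 12/21 = 57% |
| 12 (assumed) | 6/18 = 33% | 12/24 = 50% |

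**Step 3: example with a = 9, b = 6.** Rates are in arbitrary points per month and are assumed.
- Complete halt, u = 1.0, v = 0: D = 9 × 1.0 + 0 = 9.
- No effect, u = v = 0.6: D = 15 × 0.6 = 9, the same value.
- Halved rate, u = 1.0, v = 0.5: D = 9 + 3 = 12.
- No effect, u = v = 1.0: D = 15.

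**Step 4: what two-visit patients can contribute.** Within one patient, two visits give one difference and two unknown slopes. Pooled over patients with patient intercepts, common slopes and visit noise of SD s:
- All patients at −9 and +6: the information matrix for the two slopes has determinant 0, so v − u cannot be estimated.
- 5 patients at −9, 0 and +6: standard error of v − u is 0.153s.
- The same 5 plus 25 patients all at −9 and +6: 0.152s.
- The same 5 plus 25 two-visit patients with first visits spread uniformly over −12 to −6 (assumed): about 0.120s with post visits spread over +6 to +12, and about 0.127s over +3 to +9.

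Two-visit patients therefore help only if their visit times differ.

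**Step 5: precision using three-visit patients only.** For segments of length A (first visit to initiation visit) and B (initiation visit to post visit), the SD of one patient's slope difference is s·√(1/A² + (1/A + 1/B)² + 1/B²). The 95% half-width is t(0.975, n−1)·SD/√n.
- Visits at −9, 0, +6 (A = 9, B = 6): SD 0.342s; half-width 2.776 × 0.342s/√5 = 0.43s with 5 patients, 0.25s with 10.
- Visits at −9, +3, +6 (A = 12, B = 3): SD 0.540s; half-width 0.67s with 5 patients, 0.39s with 10.
- Adding an assumed between-patient SD of 0.2s in the slope difference: 0.49s and 0.72s with 5 patients.

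**Step 6: contamination from the ±3-month initiation window.**
- Initiation visit at −3: 3/9 = 33% untreated time in a segment ending at +6, and 3/6 = 50% in one ending at +3.
- Initiation visit at +3: 3/15 = 20% to 3/9 = 33% treated time in the pre-treatment segment.
- Initiation and post visits both at +3: no on-treatment segment remains.

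**The case against.** The strongest defence is that the fallback fits the objective, which asks about function before and after initiation. The SAP nowhere calls the fallback result a rate, a slowing or a drug effect. A reader might infer that it presents the t-test as a test of slowing, and the text does not support that. What stands is narrower: the question changes from that of the main model without notice, and a p-value is attached.

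A reader might also infer that the plan never separates the two periods outside the main model. It does so in part. The shift table in SAP 7.1.3 is a firm commitment and takes on-treatment change from the initiation visit. But it is descriptive, covers only PND and CMTNS2, and leaves out NIS-CS, NIS-LL, MRC and mBMI. The summaries by window in the same section are optional and at population level. SAP 7.1.2 also promises descriptive change from baseline, but its reference is unclear: baseline is within 3 months of initiation in Protocol 9.2.1 and the SAP covariate footnote, while SAP 2.1 and 7.1.3 use pre-treatment baseline for the earlier window.

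A third inference would be that two-visit data can never separate two rates. That is true within a patient or when visit times coincide. Step 4 shows that it is not true in general under common slopes.

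Finally, the fallback may never be used. The Protocol section 5 remark that most patients are not expected to have multiple measures before or after treatment does not make it likely, because one visit in each of the three windows already meets the model's minimum. This stands.

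**Conclusion.** The point holds as a gap in a contingency analysis. For an eligible patient the first fallback compares a value at −12 to −6 months with one post-treatment value, and the difference adds untreated and on-treatment change. With the post visit at +6 months, 50% to 67% of the interval is untreated. The result can describe function at two times, but it cannot show whether progression slowed, and pairing the test would not change that.

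The shares follow from the study windows. The claim that a complete halt still shows as worsening assumes that patients were worsening before treatment. The point values in Step 3 are illustrative and tied to no scale: a 9-point change is impossible on a single 0 to 5 MRC grade, for example.

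How often this matters is unknown. Under the protocol criterion of one assessment before and one after, the fallback can arise. Under the SAP criterion of two after, every eligible patient has three assessments, so it would arise only from missing scale data. The change should be made, but the documents do not support saying that the main analysis is affected or that the fallback is the expected analysis.

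**What to change.** 1. Define the first measurement as the pre-treatment assessment (−12 to −6 months). Use the initiation assessment (±3 months) as the reference for on-treatment change in the continuous scores, as the shift table already does. Reconciling the two assessment-count criteria would settle when the fallback can arise.
2. In the fallback, estimate monthly change before and after initiation from actual visit dates, with a 95% confidence interval for the difference. Do this within patient for those with all three assessments. As a sensitivity analysis, fit a two-slope mixed model with patient intercepts and common slopes that keeps the two-visit patients.
3. Label any first-to-post difference, including the two-assessment t-test in the second fallback, as mixed untreated and treated time. Give the months on each side of initiation, and state that it does not test slowing or a tafamidis effect.

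**Cost.** SAP wording and a little programming on assessments that the plan already extracts. The within-patient comparison rests on the group that triggered the fallback by being small, so its interval will be wide (Step 5). The initiation window leaves some contamination (Step 6). The mixed model depends on a common-slope assumption and gains little if visit times are alike. For two-visit patients with similar timing, the only gain is correct labelling.

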## 2.1. Study Design

This will be an observational, retrospective cohort study using structured secondary anonymized data. Patients with mixed-phenotype ATTRv-CM receiving tafamidis, as either VYNDAQEL 80 mg (four 20-mg tafamidis meglumine capsules) orally once daily or VYNDAMAX 61 mg (one 61-mg tafamidis capsule) orally once daily for at least 6 months, will be identified. Relevant data will be extracted through at least 6 months following the initiation of tafamidis treatment (with a ±3-month window).

The index date of this study is defined as the date of tafamidis treatment initiation with at least 6-month (and up to 12 months) pre-index period as the study pre-treatment baseline. Patients will be followed from index date for at least 6 months post-treatment (with a  $\pm 3$ -month window).

This study also includes three assessment windows in which the study endpoints will be extracted and evaluated. The pre-treatment assessment will be extracted at least 6 (and up to 12 months) prior to treatment initiation. The tafamidis initiation assessment will be obtained 3 months before or 3 months after the start of tafamidis treatment. The post-treatment endpoints will be assessed at least 6 months after (with a  $\pm 3$ -month window) treatment initiation.

The final study design will be determined based on feasibility assessment.

[figure not shown]

Figure 1. Overview of Study Design

\*Charcot-Marie-Tooth neuropathy score v2 (CMTNS2); mBMI: Modified body mass index; MRC: Medical Research Council; NIS-CS: Neuropathy impairment score-composite score; NIS-LL: Neuropathy impairment score-lower limbs; PND: Polyneuropathy disability.

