#### 6. HANDLING OF MISSING VALUES

For NIS-CS and NIS-LL neurologic progression endpoints, two assessments (one for left side, one for right side of body) should be reported for each muscle group or sensation area for motor strength/weakness, muscle stretch reflexes, and sensation subscales for each patient at the relevant timepoint. If the score on the left side of the body for a specific group/area is missing, and the score on the right is not missing, then the score on the right side could be used as score for the left side. The imputation could be applied vice versa. No further imputation will be performed when calculating final NIS-CS and NIS-LL total scores.

For mBMI, the pre-treatment value can be used to impute the missing post-treatment value for the same patient.

No missing data imputation will be performed for other neurologic progression or overall health endpoints.

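### The two-assessment fallback takes its post-treatment value from whichever window most patients happen to have a visit in, and gives no rule for eligible patients seen only outside it

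*SAP*

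**What the plan says.** SAP 7.2 plans a linear mixed-effect model for patients with at least three assessments. The fallback applies "if there is not a sufficient number of patients with at least three neurologic assessments, and many patients only have two assessments"; no number defines sufficient. It pairs the first measurement with "the measurement that fell within the window of the measurement in which majority of the patients had for the post-treatment assessment", and the plan is to "test for significant statistical differences between the two assessments using an unpaired, or independent samples, t-test".

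The timing rules around it are loose:

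- SAP 7.1.3: "More details of the number of assessments and assessment schedule will be finalized once the data structure is known".
- Protocol 9.2.1, footnote to criterion 4: "The post-treatment period will be at least 6months after treatment initiation". No upper limit is given, and one post-treatment assessment is enough for eligibility.
- SAP 2.1: "The post-treatment endpoints will be assessed at least 6 months after (with a", followed by a window of plus or minus 3 months. Whether this caps the period or only softens its start is not stated.

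On missing values, SAP 6 allows left/right substitution within the NIS scores and then says "No missing data imputation will be performed for other neurologic progression or overall health endpoints". mBMI is treated differently: "For mBMI, the pre-treatment value can be used to impute the missing post-treatment value for the same patient". The closing part of SAP 7.2 expects some patients to be unusable for the pre/post comparison and gives them descriptive statistics only.

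**The concern.** The window can be known only after the visit dates have been counted. A patient can meet every protocol criterion, have an observed pre/post pair, and still have no value in that window. The SAP offers no nearest-visit rule, no last-value rule and no sensitivity analysis for such a patient.

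The route is a likely one. The reason recorded for Protocol Amendment 1 is that most patients are not expected to have multiple measures before or after treatment, and a patient with a single post-treatment visit is exactly the one exposed to this rule.

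At stake is observed, eligible data from a cohort of about 30. Membership of the tested group would depend on when routine visits took place. If visit timing is linked to how fast patients worsen, the estimated change is also biased.

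**Working it through.** The plan has no design calculation to reproduce. Protocol 9.5 makes no formal sample size calculation, and the figure of at least 30 (also in SAP 4.1) is an estimate. Alpha is 0.05 two-sided (SAP 3.2).

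**1. How many second values can be lost.** The smallest strict majority of 30 is 30/2 + 1 = 16. Up to 30 − 16 = 14 patients (14/30 = 47%) can lie outside the window. This is the arithmetic worst case, not a forecast.

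**2. Effect on the standard error.** With a common SD, the unpaired standard error is proportional to sqrt(1/n1 + 1/n2).

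- First values kept for all 30: sqrt[(1/30 + 1/16)/(2/30)] = sqrt(1.4375) = 1.20.
- Both values dropped for the 14: sqrt(30/16) = 1.37.

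**3. What that means for the test.** The difference detectable at 80% power is (1.960 + 0.842) × sqrt(1/n1 + 1/n2), in SD units. Power is for an assumed difference of 0.5 SD. Both treat the two columns as independent, as the planned test does.

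| n1 / n2 | Detectable difference | Power at 0.5 SD |
|---|---|---|
| 30 / 30 | 0.72 SD | 0.49 |
| 30 / 16 | 2.802 × 0.3096 = 0.87 SD | 0.37 |
| 24 / 24 | 0.81 SD | 0.41 |
| 20 / 20 | 0.89 SD | 0.35 |
| 16 / 16 | 0.99 SD | 0.29 |

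**4. Bias.** If the omitted patients' mean change differs from that of the retained patients by D, the retained mean misses the all-patient mean by (share omitted) × D. The documents give no D, so the values here are assumptions. With 14 of 30 omitted:

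- D = 0: no bias.
- D = 6 NIS points more worsening in those omitted: progression understated by 14/30 × 6 = 2.8 points.
- D = 6 points less worsening in those omitted: progression overstated by 2.8 points.

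A simulated logistic selection model gives the same picture. It assumes a true mean worsening of 0.50 SD of change, with 80%, 67% or 53% of patients in the window.

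| Odds ratio of an in-window visit per SD of worsening | Mean change in window (80%, 67%, 53%) |
|---|---|
| 1.00 | 0.50, 0.50, 0.50 |
| 0.61 | 0.41, 0.34, 0.28 |
| 0.37 | 0.33, 0.22, 0.12 |

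Progression is thus understated by 0.10 to 0.39 SD when faster progressors are less often in the window. By symmetry, the reciprocal odds ratios give errors of the same size in the other direction.

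**5. Can eligible patients fall outside the window under either reading of the SAP?** If the post-treatment period is open-ended, the majority window may lie anywhere from month 6 onward, and patients seen earlier or later miss it. If the SAP means months 3 to 9, a majority window around a yearly visit is impossible. A patient seen only after month 9 still meets the protocol criterion and still has no value.

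**The case against.** Several counter-arguments carry weight.

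- **The SAP does not say that anyone is dropped.** That is correct. The loss is inferred from silence: no value in the window, no substitute visit, no imputation. Because the test is unpaired, first values could stay in. That gives the smaller factor of 1.20, but leaves different patients in the two columns. For mBMI the pre-treatment value may be carried forward, so those patients need not be lost.
- **A majority is a count of dates, not of results.** A reader might infer that the window is picked to suit the outcome. Nothing in the documents supports that. SAP 7.1.3 refers to the structure of the data, and SAP 2.1 ties the final design to a feasibility assessment.
- **Early leavers are partly dealt with elsewhere.** Patients treated for less than 6 months (3 on one reading of the SAP window) are already excluded by the treatment-duration criterion. Others may appear in the descriptive tables. They are still absent from the test.
- **The direction of bias is not known.** It is tempting to conclude that early leavers vanish and the result flatters tafamidis. The documents do not show it. In a progressive disease, patients seen early have had less time to worsen, so at equal monthly rates omitting them makes the mean raw change look worse. If the window lies near month 6, it is the later attenders who are omitted.
- **Reach is limited.** The rule applies only if the mixed model is not used, SAP 7.2 offers a second alternative, and the study is exploratory. SAP 2.1.1 also lists at least two post-treatment assessments, which would give every patient three. However, SAP 4.1 defines the full analysis set by the protocol criteria, which require one, and SAP 3.1 still reports p-values at the 0.05 level.

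A common window does limit variation in follow-up, which is a fair reason to keep it as a secondary analysis.

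**Conclusion.** The point holds in a limited form. As written, the fallback leaves eligible patients without a second value in the neurologic tests solely because of when they were seen, in a window that is not stated in months.

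The worst case is 14 of 30 patients (47%), with the standard error up by 1.20 or 1.37 depending on whether first values are kept. This rests on exactly 30 patients and a bare majority; a larger share in the window reduces the loss.

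The bias figures are illustrations only. Bias is zero if visit timing is unrelated to progression, and its sign cannot be established from the documents. The plan should therefore not be read as one that favours the drug. The defect is an avoidable loss of observed data under a rule still to be settled, and it merits a change to the SAP.

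**What to change.** In SAP 7.2, before outcome scores are examined:

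1. Replace the majority-window rule with a per-patient rule: the post-treatment value is the eligible post-treatment assessment closest to 6 months after initiation, the plan's own anchor, so that no eligible patient is left out because of visit timing. Add a tie rule, and reconcile the protocol and SAP on when the post-treatment period starts and whether it ends.
2. Analyse the within-patient change instead of two independent columns. Include time from first measurement to initiation and time from initiation to the post-treatment assessment, for example as covariates. Do not divide by total elapsed months, because that mixes untreated and treated time. A first value 12 months before and a second 6 months after initiation span 18 months, of which 6/18 = 33% are treated; 6 months before and 12 after also span 18, with 12/18 = 67% treated.
3. Keep the majority-window analysis as a sensitivity analysis. Report how many patients fall outside that window, with reasons and baseline scores.

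The cost is SAP text covering both the visit rule and the test, with no new data. Follow-up time will vary more between patients, which the time covariates address only in part, and two covariates use some information in a sample of about 30.
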